Abbreviations used in this table may be found in Appendix 13 .	Day -28 to Day-1	Day 1 (fasted)	Day 4 (fasted)	Day 7 (fasted)	Day 15 (fasted)	Day 28	Day 84 (fasted)	Day 168 (fasted)	Day 252 (fasted)	Day 364 (fasted)		
 Day relative to start of study intervention (Day 1).
Visit Window						±3 d	±5 d	±5 d	±5 d	±3 d		
 See Section 8.4.3 for follow-up AE and SAE assessments.
EGD with biopsy (Substudy Only)	X									X		
 For participants in Biopsy Substudy Only. The EGD with biopsy will be performed once all other inclusion criteria are met. Biopsy must be collected at least 4 days prior to dosing (Day 1). Approximately 6 duodenal biopsies. For rescreening: EGD with biopsy does not need to be repeated unless >3 months have elapsed from last assessment.
Gluten Challenge					X		X	X	X			
 See Section 8.2.1 for additional information. Participants who withdraw from treatment and do not receive 3 full doses should not receive GC.
PD Assessments												
 See Section 8 for additional information.
Plasma IL-2 biomarker					X		X	X	X			
 See Section 8.2.2 for additional information. At every GC visit, plasma IL-2 sample should be collected at least 5 minutes before and 4 hours (± 15 minutes) after GC. Participants who withdraw from treatment and do not receive 3 full doses should not have plasma samples collected.
Other plasma biomarkers		X	X	X								
 See Section 8.7 for additional information. At every dosing visit, plasma samples should be collected at least 5 minutes before and 4 hours (±15 minutes) after dosing. Additional plasma samples should be collected as soon as practically feasible, in an event of treatment emergent, clinically significant orthostatic hypotension, syncope, or treatment-related TEAE, Grade 3 or above. Participants who withdraw from treatment and do not receive 3 full doses should not have plasma samples collected.

090177e19fcc12ed\Approved\Approved On: 30-Jan-2024 19:45 (GMT)

Visit Identifier	Screen	Treatment Period			Follow-Up Period						ET	Notes
					GC	FU W4	GC W12	GC W24	GC W36	FU W52		

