4. ANALYSIS SETS

For purposes of analysis, the following analysis sets are defined for Part C:

Analysis Set	Description
Entered	All participants who sign the ICD.
Enrolled (Randomized or assigned to study intervention)	All entered participants who are randomized to study intervention in Part C.
Full analysis set (FAS)	All participants who are randomly assigned to study intervention and receive any portion of study intervention in Part C. Participants will be analyzed according to the intervention they are randomized.

Analysis Set	Description
Safety analysis set (SAS)	All participants who receive any portion of study intervention in Part C. Participants will be analyzed according to the intervention they actually received.
PK analysis set (PKAS)	All participants who receive any portion of study intervention and have at least one concentration value in Part C.

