6.5.4. Gluten Challenge

GC will be summarized by number and percentage of participants completed GC at each GC scheduled timepoint for SAS.

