6.6. Safety Summaries and Analyses

Safety analyses will be based on the SAS.

All clinical TEAEs, SAEs, withdrawal due to AEs, vital signs and safety laboratory data will be reviewed on an ongoing basis during the study to evaluate the safety of participants.

Safety data will be presented in tabular and/or graphical format and summarized descriptively, where appropriate. All safety endpoints will be listed and summarized in accordance with Sponsor's Standards. Categorical outcomes (eg, AEs) will be summarized by participant counts and percentage. Continuous outcome will be summarized using N, mean, median, SD, min, max. Participant listings will be produced for these safety endpoints accordingly.

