6.6.1. Adverse Events

Adverse events will be summarized for SAS according to Sponsor's reporting standards for

- TEAEs
- Serious AEs (SAEs)

TEAEs will be summarized by the number of participants reporting any TEAE, system organ class (SOC), preferred term (PT), severity, relationship to investigational product.

CTCAE is used to grade the severity of AEs. TEAEs related to GC and infusion-related reactions (IRR) will also be summarized separately.

SAEs will be summarized by SOC and PT, and individual SAEs will be listed by participant.

A list of subjects who prematurely discontinue from the study due to an AE will be provided as well.

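### Gluten-challenge TEAEs are reported per treated participant, including those not allowed the challenge, so unequal early stopping could by itself separate the arms

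*SAP*

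**What the plan says.** **Denominator.** Part C SAP 6.6 states that "Safety analyses will be based on the SAS" and that "Categorical outcomes (eg, AEs) will be summarized by participant counts and percentage". Section 6.6.1 repeats the set for adverse events ("Adverse events will be summarized for SAS according to" the sponsor's reporting standards) and then adds that "TEAEs related to GC and infusion-related reactions (IRR) will also be summarized separately". It gives that separate table no denominator of its own. Section 4 defines the SAS as "All participants who receive any portion of study intervention in Part C", so having been challenged is not a condition of membership. Part B SAP 6.6.1 is worded in the same way.

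**Who is challenged.** The Part C schedule of activities (protocol 1.3.3) says: "Participants who withdraw from treatment and do not receive 3 full doses should not receive GC". Protocol 7.1 has the same rule and also keeps participants who stop study intervention in the study for safety evaluation. Protocol 7.1.2 ends challenges after a confirmed pregnancy.

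**Exposure to the challenge.** Part C SAP 6.5.4 provides one table: "GC will be summarized by number and percentage of participants completed GC at each GC scheduled timepoint for SAS". Up to four challenges are planned in Part C (protocol 2.3.1): Day 15 and Weeks 12, 24 and 36.

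**The concern.** A table of GC-related events by arm will be read as showing how each arm reacted to gluten. Protocol 8.2.1 itself separates events tied to the challenge from events tied to study drug. A participant who stops after one or two infusions and is never challenged enters that table as a person without a GC reaction, when in fact that person was not at risk of one.

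Unequal stopping is plausible, though not established. An adverse event is a listed reason for permanent discontinuation (protocol 7.1). Appendix 9 ends treatment for certain severe infusion reactions. The first-in-human study saw gastrointestinal events in more participants on drug than on placebo (protocol 2.2.3). If stopping were more common on KAN-101, part of any lower GC-reaction percentage on KAN-101 would be missing exposure that looks like tolerance. TEAE incidence is a secondary endpoint of Part C, so the table matters even though it is descriptive.

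**Working it through.** The plan states no figure for this quantity, so there is nothing of its own to reproduce. The check is an identity, followed by a range.

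**Inputs**
- Arm size: about 26, four arms, 1:1:1:1 (protocol 4.1.3).
- Denominator: the SAS (Part C SAP 4, 6.6, 6.6.1).
- Not at risk: SAS participants who withdrew from treatment without three full doses (protocol 1.3.3, 7.1).
- Risk of a GC-related TEAE among challenged participants, p: not in the documents. Assumed 40%, 60% or 80%.
- Number not challenged in an arm, k: not in the documents. Assumed 0 to 8 of 26.

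**Formula**

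Reported SAS percentage = p × (26 − k) / 26

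The multiplier is 25/26 = 0.962 at k = 1, 24/26 = 0.923 at k = 2, 22/26 = 0.846 at k = 4 and 18/26 = 0.692 at k = 8.

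| Assumed p | k = 0 | k = 1 | k = 2 | k = 4 | k = 8 |
|---|---|---|---|---|---|
| 40% | 40.0% | 38.5% | 36.9% | 33.8% | 27.7% |
| 60% | 60.0% | 57.7% | 55.4% | 50.8% | 41.5% |
| 80% | 80.0% | 76.9% | 73.8% | 67.7% | 55.4% |

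**Reading the table**
- *Equal risk, unequal stopping.* At p = 60% with k = 4 in one arm and k = 0 in the other: 0.60 × 22/26 = 50.8% against 60.0%, a gap of 9.2 points with no difference in reaction to gluten. The same gap is 6.2 points at p = 40% and 12.3 points at p = 80%.
- *Small numbers stopping.* One or two stops lower an arm by 1.5 to 3.1 points at p = 40% and by 3.1 to 6.2 points at p = 80%.
- *Order of the arms.* Placebo at 50% with k = 0 shows 50.0%. An active arm at 60% with k = 5 shows 0.60 × 21/26 = 48.5%. The order reverses.
- *Equal stopping.* The same k in every arm applies the same multiplier to each, so arms with equal risk show equal percentages.

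**Does another planned output repair this?** Only in part. The table in section 6.5.4 counts completers. Protocol 8.2.1 defines compliance as finishing the whole 9 g, container washes included, within about 15 minutes. A participant who starts, reacts and cannot finish was exposed but is not a completer. The TEAE summary by treatment period in protocol 9.3.3 is not carried into Part C SAP 6.6.1, and SAP 2.1 does not list its omission as a change.

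**The case against.** The strongest case against the point has five parts.

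1. *The bias is conditional.* A reader might infer that arms with more dosing reactions will show falsely few challenge reactions. The documents do not support that. They give no stopping or reaction rates for Part C. Appendix 9 provides for further infusions after Grade 1 and 2 reactions and some Grade 3 reactions, and protocol 6.1.1 permits premedication. Part C dropped the screening challenge suspected of causing the Part B reactions, and those reactions were reported blinded. This objection stands: more reactions need not mean more stopping, and stopping need not differ by arm.
2. *The SAS percentage is a legitimate quantity.* It is the incidence per treated participant. This stands, and is why it should be kept. It misleads only when read as the risk of reacting to a challenge.
3. *A challenged-only rate is not the true rate.* Starting a challenge is a post-randomisation event. If the most reactive participants stop early, those left are more tolerant, and this too could look like protection. This stands, and rules out replacing one rate with the other.
4. *A reader could re-base the figure.* Completers, doses received, disposition and listings are all planned. This stands only roughly, because completers are not starters and the tables are not linked.
5. *The table is descriptive and the arms are small.* Gluten response is measured by Day 15 IL-2. At p = 60% the standard error of a two-arm difference is √(2 × 0.60 × 0.40 / 26) = 13.6 points, larger than the 9.2-point example. This limits the weight of the point. It does not remove it, since the dilution is systematic whenever stopping is unequal.

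The sponsor's reporting standards might set another denominator, but none is stated.

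**Conclusion.** The point holds in conditional form. By the text of the Part C SAP, the GC-related percentage mixes two things: the risk among challenged participants and the share challenged. If early stopping differs by arm, the arm with more stopping may show a lower figure for that reason alone. Under assumed rates the effect runs from about 2 to 6 points for one or two stops in an arm of 26 to about 6 to 12 points for four. It is nil between arms of equal risk when stopping is equal.

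Two wider readings should not be drawn:
- A missed visit does not end challenges. Protocol 7.3 asks the site to reschedule it. Pregnancy does end them, but nothing suggests that this differs by arm.
- Participants may have had different numbers of challenges when the study was terminated. That follows enrolment timing, which randomisation balances in expectation. It is a reason to tabulate by challenge, not evidence of bias between arms.

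This is a worthwhile correction to a safety table. It does not affect the primary analysis.

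**What to change.** In Part C SAP 6.6.1, and for consistency in Part B SAP 6.6.1:

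- Keep the SAS percentage for GC-related TEAEs.
- Beside it, report GC-related TEAEs for each challenge (Day 15 and each later challenge performed), with SAS participants who started that challenge as the denominator.
- Show by arm how many SAS participants were not challenged at that timepoint, and why.
- Label the added percentage as descriptive, in a post-randomisation subset, and not a randomised comparison.
- Leave the SAS denominator unchanged for dosing-related events and infusion-related reactions.

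The cost is a change to table specifications. The challenge is taken on site under staff observation (protocol 8.2.1), so no new data should be needed, assuming that starting a challenge is recorded as well as completing it. The drawback is a second percentage that needs its caveat. In Part B, with about 4 participants per group, counts will say more than percentages.

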6.6.2. Safety Laboratory Data

Clinical safety laboratory values and change from baseline and clinical significant change will be summarized according to Sponsor's standards.

6.6.3. Vital Signs

Vital signs and change from baseline and clinical significant change will be summarized according to Sponsor's standards.

7. INTERIM ANALYSES

An interim analysis (IA) may be conducted and results may be used to inform internal decisions regarding future study planning.

Before any IA is performed, the details of the objectives, decision criteria, dissemination plan, and method of maintaining the study blind as per the sponsor's SOPs will be documented and approved in a DSMB charter.

In addition, DSMB will review unblinded safety and PK data periodically and make recommendations for study continuation as defined in the DSMB charter.

8. REFERENCES

1. Protocol KAN-101-02.

APPENDICES**Appendix 1. Summary of Efficacy Analyses**

Endpoint	Analysis Type	Population	Data Inclusion and Rules for Handling Intercurrent Events and Missing Data	Analysis Model
Change in IL-2 from pre-GC to post-GC at Day 15	Summary	FAS	Observed cases, no imputation for missing data.	N/A
	Main analysis	FAS	Data collected after intercurrent events will be excluded. Missing data will not be imputed.	ANCOVA with terms treatment, pre-GC IL-2 at Day 15
	Sensitivity/supplementary analysis	FAS	All data collected will be included regardless of intercurrent events. Missing data will not be imputed.	ANCOVA with terms treatment, pre-GC IL-2 at Day 15
CDS D (Each item and question of the CDS D as well as the CDS D Total Score, CDS D Gastrointestinal (GI) Score) change from baseline at each timepoint	Summary	FAS	Observed cases, no imputation for missing data.	N/A
CDS D 1-Day, 3-Day, 7-Day Nausea Score and Vomiting Frequency and change from baseline at each timepoint post-gluten challenge	Summary	FAS	Observed cases, no imputation for missing data.	N/A

Endpoint	Analysis Type	Population	Data Inclusion and Rules for Handling Intercurrent Events and Missing Data	Analysis Model
PGIS change from baseline at each timepoint	Summary	FAS	Observed cases, no imputation for missing data.	N/A
PGIC at each timepoint	Summary	FAS	Observed cases, no imputation for missing data.	N/A

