For Part A, the primary endpoint is incidence and severity of TEAEs as assessed by CTCAE.

For Part B, the primary endpoint is change in magnitude of IL-2 response pre- and post-GC in peripheral blood from baseline screening to Day 15.

For Part C, the primary endpoint is the change in IL-2 from pre-GC to post-GC on Day 15 in participants treated with KAN-101 versus PBO.

Main Analytical Approach:

- **For Part A**, number and percent of participants with TEAEs will be summarized by cohort, SOC, PT, and severity.
- **For Part B**, the primary endpoint will be descriptively summarized by treatment using Estimand 1 for FAS. There is no statistical hypothesis testing.
- **For Part C**, change in IL-2 from pre-GC to post-GC on Day 15 will be analyzed using ANOVA model.
 - The main analysis of the primary endpoint will be based on Estimand 2 using FAS. The LSM difference of the change from pre-GC to post-GC on Day 15 (log transformed) between each KAN-101 group and PBO will be provided; prohibited medications, incomplete GC at Day 15, and discontinuation of study intervention are intercurrent events. All data collected after any intercurrent events will be excluded.
 - All statistical tests will be 2-tailed at a $\alpha = 0.05$.

Secondary Endpoint Analysis

For Part A, PK concentration and PK parameters will be descriptively summarized by treatment group.

[figure not shown]
For Part B and Part C, number and percent of participants with TEAEs will be summarized by treatment, SOC, PT, and severity. PK concentration and PK parameters will be descriptively summarized by treatment group. Number of TEAEs (all-causality and treatment-related) and percent of participants with TEAEs will also be summarized by treatment period, treatment, SOC, PT, and severity.

Ethical Considerations:

The overall potential benefit/risk of KAN-101 is considered favorable. Taking into account the measures to minimize risk to study participants, the potential risks identified in association with KAN-101 are justified by the anticipated benefits that may be afforded to participants with CeD.

[figure not shown]

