9. STATISTICAL CONSIDERATIONS

Detailed methodology for summary and statistical analyses of the data collected in this study is outlined here and further detailed in the SAP, which will be maintained by the sponsor. The SAP may modify what is outlined in the protocol where appropriate; however, any major modifications of the primary endpoint definitions or their analyses will also be reflected in a protocol amendment.

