9.3.1.1. Analyses for Continuous Endpoints

For continuous endpoints in Part C, the change from baseline will be analyzed by timepoint using ANCOVA model with treatment as the factor, baseline as a covariate. Endpoints without baseline will be analyzed by ANOVA with treatment as the factor. Comparison of

KAN-101 to PBO (providing LSM of the treatments, LSM of the treatment difference, p-value and 95% CI) will be generated.

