9.3.4. Tertiary/Exploratory Endpoints Analysis

Results of exploratory endpoint analyses will be utilized for internal purposes and may not be described in the CSR.

For Part A,

- Change in magnitude of IL-2 response pre-and-post GC in in peripheral blood at Day 15 will be descriptively summarized by cohort.
- KAN-101 PK parameters, as data permit: AUC_{inf} (dn), AUC_{last} (dn), C_{max} (dn), CL, V, for analysis details see [Section 9.3.5](#).
- Incidence of development of ADA during the study, for analysis details see [Section 9.3.7](#).

For Part B,

- PRO will be summarized to track CeD symptoms over the duration of the study for FAS. Further details will be provided in the SAP.
- Change in magnitude of IL-2 response pre- and post-GC in peripheral blood from baseline (run-in) to GC at Weeks 12, 24, and 36 will be descriptively summarized by timepoint for FAS.
- Change in magnitude of IL-2 response pre- and post-GC in peripheral blood from Day 15 to Weeks 12, 24, and 36 will be descriptively summarized by timepoint for FAS as well.
- KAN-101 PK parameters, as data permit: AUC_{inf} (dn), AUC_{last} (dn), C_{max} (dn), CL, V, for analysis details see [Section 9.3.5](#).
- Incidence of development of ADA during the study, for analysis details see [Section 9.3.7](#).

For Part C,

- PRO will be analyzed using ANCOVA model by timepoint for FAS. Further details will be provided in the SAP.
- Change in circulating levels of IL-2 from pre-GC to post-GC at Weeks 12, 24, and 36 will be analyzed using ANOVA model by timepoint for FAS.
- Change in circulating levels of IL-2 from pre-dose to post dose on Days 1, 4, and 7 will be analyzed using ANOVA model by timepoint for FAS.
- Change in circulating levels of IL-2 pre- and post-GC from Day 15 to Weeks 12, 24, and 36 will be analyzed using ANOVA model by timepoint for FAS.
- KAN-101 PK parameters, as data permit: AUC_{inf} (dn), AUC_{last} (dn), C_{max} (dn), CL, V, for analysis details see [Section 9.3.5](#).
- Incidence of development of ADA during the study, for analysis details see [Section 9.3.7](#).

For Part B and Part C substudy,

- Change from baseline in histology (including, but not limited to, Marsh score, villous height crypt depth ratio, IEL counts) at Week 52 will be summarized by treatment for biopsy substudy.
- Correlation between histological state, symptomatic response (PRO data) and biomarker responses (IL-2) will be provided.

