1. VERSION HISTORY

This Statistical Analysis Plan (SAP) for study KAN-101-02 Part C is based on the protocol amendment dated 30Jan2024.

Table 1. Summary of Changes

Version/Date	Associated Protocol Amendment	Rationale	Specific Changes
1 28Feb2024	Amendment 3 30Jan2024	Not Applicable (N/A)	N/A
2 05SEP2024	Amendment 3 30Jan2024	Added summary and analysis for Nausea Score and Vomiting Frequency and change from baseline	Sections 3.3 and 6.5.4.1, CDSD 1-Day, 3-Day, 7-Day Nausea Score and Vomiting Frequency and change from baseline at each timepoint post-gluten challenge will be summarized and analyzed using Wilcoxon Signed-rank test for within treatment paired comparison and Wilcoxon Rank Sum test for comparison between placebo vs each of KAN group.
3 13DEC2024	Amendment 3 30Jan2024	Made clarification for baseline, 3-day and weekly average calculation and timepoints. Marsh score is categorical	Sections 3.3 and 6.4.5.1, CDSD average score calculation and analysis timepoint were updated. Section 6.4.6.1, Screening and Week 52 Marsh score will be summarized with frequency and percentage. Change from screening to Week 52 will be summarized using shift table

Table 1. Summary of Changes

Version/Date	Associated Protocol Amendment	Rationale	Specific Changes
		Define IL-2 and CDS analysis window	Appendix 2.1, Table 7 was added for IL-2 and CDS analysis window.
4 13Jun2025	Amendment 3 30Jan2024	Study termination	Sections 6.3.1, 6.3.3, 6.3.4 and 6.3.5, 6.3.7 exploratory endpoints and biopsy substudy endpoints will not be measured/reported. Section 6.3.6, descriptive summary for PRO endpoints will be performed for data up to Week 12.

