2.1. Modifications to the Analysis Plan Described in the Protocol

“Entered” analysis set is added to [Section 4](#), it is not in the protocol. The definition of “Enrolled” analysis set is different from that in the protocol.

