5.2.1. Analyses for Continuous Endpoints

For continuous endpoints in Part C, the change from baseline will be analyzed by timepoint using analysis of covariance (ANCOVA) model with treatment as a factor, baseline as a covariate. For endpoints without baseline, analysis of variance (ANOVA) model with treatment as a factor will be used for the analysis. Comparison of each dose group of KAN-101 to PBO (providing LSM of the treatments, LSM of the treatment difference, p-value and 95% CI) will be generated.

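### Part C primary endpoint: the SAP fits ANCOVA on a post-dose covariate where the protocol specifies treatment-only ANOVA, and SAP 2.1 does not declare the change

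*SAP*

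**What the plan says.** **Protocol.** The synopsis says of Part C that "change in IL-2 from pre-GC to post-GC on Day 15 will be analyzed using ANOVA model", and section 9.3.2.2 repeats this, pointing to 9.3.1.1. There the rule is: "Endpoints without baseline will be analyzed by ANOVA with treatment as the factor". Section 9.3.4 takes the same approach at the later challenges: "Change in circulating levels of IL-2 from pre-GC to post-GC at Weeks 12, 24, and 36 will be analyzed using ANOVA model". For the sensitivity analysis, 9.3.2.3 names the treatment-policy estimand but no model, and leaves the details to the SAP.

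**SAP Part C.** Section 6.1.1 (main) and 6.1.2 (treatment policy) both name ANCOVA and refer to 5.2.1. Appendix 1 gives the terms, identically in both rows: "ANCOVA with terms treatment, pre-GC IL-2 at Day 15". Section 5.2.1 ties ANCOVA to change from a baseline and otherwise says: "For endpoints without baseline, analysis of variance (ANOVA) model with treatment as a factor will be used". No IL-2 baseline is defined for Part C.

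**Declaration.** SAP 2.1, the section for departures from the protocol, covers only the added Entered set and the fact that the Enrolled "analysis set is different from that in the protocol". The primary model is not mentioned.

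**Estimands.** Estimands 2 and 3 (SAP 2.2.1 and 2.2.2) both take as their summary the least-squares-mean difference, each dose against placebo, in the log change across the challenge.

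**The concern.** Two different primary models are on file for one endpoint, and the section meant to list departures is silent. A reader who holds the protocol would expect the reported difference to be a plain difference in mean log change. The SAP would give a covariate-adjusted difference instead.

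The covariate is the reason this is more than wording. Adjusting for a pre-randomisation value leaves the target of a comparison of mean change unchanged, because randomisation balances that value in expectation. Day 15 pre-GC IL-2 lacks that protection, since it is drawn after all three doses. If treatment moves it, the adjusted contrast is no longer the quantity that Estimands 2 and 3 name. Both inferential analyses carry the same covariate, so comparing them cannot show whether the result depends on it. SAP 6.1 plans geometric means and ratios by arm, from which an unadjusted contrast can be read, but with no between-arm interval or test.

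**Working it through.** **1. Timing.** Dosing is on Days 1, 4 and 7 and the covariate is drawn on Day 15: 15 - 7 = 8 days after the last dose. The Part C schedule lists plasma IL-2 at GC visits only, the first being Day 15. Protocol 9.3.4 does refer to pre-dose IL-2 on Day 1, whereas the schedule and objectives list other biomarkers there. Either way, the SAP neither defines such a value as a baseline nor uses it.

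**2. The plan's own figure.** Protocol 9.5 gives difference 2.37, SD 1.53, 26 per group, two-sided 5%, power 99%.
- SE = 1.53 x sqrt(2/26) = 0.424; 2.37/0.424 = 5.6.
- Non-central t power: 99.98% (df 50 or df 100).

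The stated power is met, and the choice of model does not threaten it.

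**3. What each model estimates.** SAP 6.1 logs each IL-2 value before modelling, so I take the covariate as logged too. Let D be the between-arm difference in mean change, d the treatment shift in mean log pre-GC IL-2, and b the within-arm slope of log post-GC on log pre-GC. The slope of change on pre-GC is b - 1, so

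ANCOVA contrast = D - (b - 1)d = D + (1 - b)d.

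ANOVA estimates D. The two agree if d = 0 or b = 1. Neither d nor b is in the documents.

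**4. If d = 0** (assumed pre-GC SD 0.5 / 0.75 / 1.0; four arms of 26; 10,000 simulated trials per cell). Both models reject in about 5% under no effect. Mean SE of one dose against placebo is 0.42 for ANOVA, and for ANCOVA:

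| b | SE |
|---|---|
| 0 | 0.402 / 0.371 / 0.322 |
| 0.3 | 0.415 / 0.399 / 0.378 |
| 0.5 | 0.420 / 0.413 / 0.402 |
| 0.8 | 0.424 / 0.423 / 0.422 |
| 1 | 0.425 |

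**5. If d is not 0: illustration only.** Same set-up, D = 0, assumed d = -0.5 in every active arm:

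| b | Offset (1 - b)d | ANCOVA rejects |
|---|---|---|
| 0 | -0.50 | 21.4 / 25.7 / 32.8% |
| 0.3 | -0.35 | 12.5 / 12.8 / 14.4% |
| 0.5 | -0.25 | 8.5 / 8.7 / 9.6% |
| 0.8 | -0.10 | 5.5 / 5.6 / 6.0% |
| 1 | 0 | 4.7 / 4.6 / 4.9% |

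ANOVA rejects in 4.7% to 5.5% throughout. With D = 0, post-GC IL-2 also shifts by d, so these are errors against the change estimand, not false positives for an inert drug. A positive d pulls the other way: at b = 0.3 and d = +0.5, a true -2.37 is estimated as -2.37 + 0.7 x 0.5 = -2.02.

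**6. The mirror case.** Suppose the drug lowers pre-GC IL-2 by 0.5 and leaves post-GC unchanged, so D = +0.50 (pre-GC SD 0.75, 6,000 trials). ANOVA then rejects in about 21% to 22%, and ANCOVA in 5.0%, 6.4% and 8.9% at b = 0, 0.3 and 0.5. ANOVA is still right for the stated estimand. The rejection rates therefore reflect which quantity is targeted; they do not rank the two models.

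**The case against.** **The SAP is allowed to differ.** Protocol section 9 says "The SAP may modify what is outlined in the protocol where appropriate", and asks for an amendment only for major modifications. Endpoint, log scale, analysis set and estimand wording are unchanged, so whether this one is major is a judgement. This stands, but it does not explain why SAP 2.1 omits the change.

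**Pre-GC can be read as the baseline of the change.** That is a natural reading of 5.2.1. It would make the protocol's ANOVA wording the thing to correct, so the documents still disagree, and a value drawn after three doses is still not protected by randomisation.

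**d is probably small.** The protocol reports a half-life of 3.74 to 36.8 minutes, no study challenge precedes the Day 15 sample in Part C, and the described effect is on the reaction to gluten. If many pre-GC values fall below LLOQ and become half LLOQ (SAP 5.3), d shrinks towards 0. This is fair though not proof, and it is why no bias is claimed. An assumed d of -0.5 is 0.5 to 1.0 of the assumed pre-GC SDs, which is a large shift.

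**If d = 0, ANCOVA is valid and may be the better model.** Agreed.

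A reader might also infer that the sensitivity analysis contradicts the protocol. It does not do so explicitly, because 9.3.2.3 leaves the model to the SAP. Nor is the SAP's Table 1 evidence of non-declaration. It logs changes between SAP versions, and if ANCOVA was already in version 1 no entry was due. Its latest entry says that "exploratory endpoints and biopsy substudy endpoints will not be measured/reported", so the protocol's ANOVA at later weeks shows intent but no longer governs a reported result.

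**Conclusion.** The mismatch is certain for the main analysis: treatment-only ANOVA in the protocol, ANCOVA on a post-dose covariate in the SAP, undeclared in SAP 2.1. It is also certain that no planned inferential analysis of this endpoint avoids the covariate. This should be fixed.

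The numerical consequence is conditional. The SAP's contrast differs from the one Estimands 2 and 3 name by (1 - b)d: nothing if d = 0 or b = 1, and up to half a log unit under the illustrated d of -0.5. It is tempting to conclude that the SAP analysis is biased or inflates false positives. The documents do not support that: they give no evidence that d is non-zero, and b, d and the pre-GC SD are all assumptions here. The sample size is not in question under either model.

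**What to change.** 1. In SAP Part C 6.1.1, 6.1.2 and Appendix 1, add the protocol's ANOVA of log post-GC minus log pre-GC IL-2, with treatment as the only term. Report the LSM difference, 95% CI and p-value beside the ANCOVA.
2. In SAP 2.1, state which model is primary and why it departs from the protocol, if it does.
3. If ANCOVA stays primary, align the wording of Estimands 2 and 3 with it, and amend the protocol only if the change is judged major. If treatment codes are already open, do not swap the primary model; declare the existing one and show the other beside it.
4. Tabulate log pre-GC Day 15 IL-2 by arm, with the share below LLOQ. The between-arm difference has SE of pre-GC SD x sqrt(2/26), or 0.14 / 0.21 / 0.28 at SD 0.5 / 0.75 / 1.0. The table can therefore show a sizeable shift but cannot prove that d = 0.

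Cost: one extra model, one table and SAP wording. No new data or participants. If ANOVA is made primary and d = 0, some precision may be lost (SE 0.42 against 0.32 to 0.42 under the assumed values), with power at 2.37 still 99.98%.
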